1. To define the safety profile of prophylactic hAd5-S-Fusion+N-ETSD in the first 200 subjects randomized (Phase 2)	In subjects receiving at least 1 dose of study intervention (safety analysis population), the percentage of subjects reporting: 
 • Local reactions for up to 7 days following each dose • Systemic events for up to 7 days following each dose • AEs from Dose 1 to 7 days after the last dose • SAEs from Dose 1 to 7 days after the last dose 	
 • Local reactions (pain at the injection site, redness, and swelling) • Systemic events (fever, fatigue, headache, chills, vomiting, diarrhea, new or worsened muscle pain, and new or worsened joint pain) • AEs • SAEs
2. To define the safety profile of prophylactic hAd5-S-Fusion+N-ETSD in all subjects randomized in Phase 2/3	In subjects receiving at least 1 dose of study intervention (safety analysis population), the percentage of subjects reporting: 
 • Local reactions for up to 7 days following each dose • Systemic events for up to 7 days following each dose • AEs from Dose 1 to 1 month after the last dose • SAEs from Dose 1 to 6 months after the last dose 	
 • AEs • SAEs • In a subset of at least 1,000 subjects: 
 ○ Local reactions (pain at the injection site, redness, and swelling) ○ Systemic events (fever, fatigue, headache, chills, vomiting, diarrhea, new or worsened muscle pain, and new or worsened joint pain)
Secondary Efficacy		
1. To evaluate the efficacy of prophylactic hAd5-S-Fusion+N-ETSD against confirmed severe COVID-19 in subjects without serological or virological evidence of infection before vaccination	In subjects complying with the key protocol criteria (evaluable efficacy population) at least 14 days after receipt of the last dose of study intervention: $VE = 100\% \times (1 - IRR) \quad [\text{ratio of active vaccine to placebo}]$	Confirmed NAAT severe COVID-19 incidence in subjects with no serological or virological evidence of past SARS-CoV-2 infection

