4. To evaluate the cellular immune stimulatory efficacy, persistence, and duration of prophylactic hAd5-S-Fusion+N-ETSD cellular immunity against confirmed SARS-CoV-2 in subjects with serological or virological evidence of infection before vaccination	Memory immune CD4 ⁺ and CD8 ⁺ T cell stimulation from baseline to specific times during the study, as noted in the Schedule of Events	
 • SARS-CoV-2 specific memory CD4⁺ and CD8⁺ T-cell stimulation to N and S proteins based on central laboratory or locally confirmed NAAT in subjects with serological or virological evidence of SARS-CoV-2 infection
5. To describe the safety, immunogenicity, and efficacy of prophylactic hAd5-S-Fusion+N-ETSD in individuals with confirmed stable HIV disease		
 • All safety, immunogenicity, and efficacy endpoints described above

^a HIV-positive and participants who develop immunosuppressive related diseases (eg, cancer, autoimmune disease) in Phase 3 will not be included in analyses of the objectives, with the exception of the specific exploratory objective.
		

Study Design:
 
This is a phase 2/3, multicenter, randomized, placebo-controlled, observer-blind study assessing the safety, tolerability, immunogenicity, and efficacy of prophylactic hAd5-S-Fusion+N-ETSD against COVID-19. The study schema is shown in Figure 1. Subjects will be ≥ 16 years of age who are healthy or have medically-stable chronic diseases and are at increased risk for SARS-CoV-2 infection and COVID-19. Approximately 20,700 subjects will be randomized in a 1:1 ratio to receive 2 subcutaneous (SC) doses of either 1×10^{11} viral particles (VP)/dose hAd5-S-Fusion+N-ETSD or placebo 3 weeks apart, on Days 1 and 22. Randomization will be stratified by age (16 to 55 years or >55 years). It is intended that a minimum of 25% of subjects will be in the >55-year stratum. Safety, immunogenicity, and efficacy assessments will be conducted per the Schedule of Events (SoE) and subjects are expected to participate for up to a maximum of approximately 2 years.
 
The first 200 subjects randomized will comprise the phase 2 portion of the study. Safety data through 7 days after Dose 2 from these 200 subjects will be analyzed by an independent statistical team and reviewed by the DMC. Enrollment may continue during this period and these subjects would be included in the phase 3 portion of the study.
		

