
Enrollment (planned):
 
Approximately 20,700 subjects will be randomized in this study.
		

Eligibility Criteria:

Inclusion Criteria:

Subjects are eligible to be included in the study only if all of the following criteria apply:

Age and Sex:

1. Male or female participants ≥ 16 years of age, at randomization.
 - Refer to [Appendix 2](#) for reproductive criteria for male and female participants.

Type of Participant and Disease Characteristics:

2. Participants who are willing and able to comply with all scheduled assessments, vaccination plan, laboratory tests, lifestyle considerations, and other study procedures.
3. Healthy participants who are determined by medical history, physical examination (if required), and clinical judgment of the investigator to be eligible for inclusion in the study.

Note: Healthy participants with preexisting stable disease, defined as disease not requiring significant change in therapy or hospitalization for worsening disease during the 6 weeks before enrollment, can be included. Specific criteria for Phase 3 participants with known stable infection with human immunodeficiency virus (HIV), hepatitis C virus (HCV), or hepatitis B virus (HBV) can be found in [Appendix 3](#).

4. Participants who, in the judgment of the investigator, are at higher risk for SARS-CoV-2 infection and subsequent development of COVID-19 (including, but not limited to, use of mass transportation, relevant demographics, and frontline essential workers).

Informed Consent:

5. Capable of giving personal signed informed consent, which includes compliance with the requirements and restrictions listed in the informed consent document (ICD) and in this protocol.

Exclusion Criteria:

Participants are excluded from the study if any of the following criteria apply:

Medical Conditions:

1. Other medical or psychiatric condition including recent (within the past year) or active suicidal ideation/behavior or laboratory abnormality that may increase the risk of study participation or, in the investigator's judgment, make the participant inappropriate for the study.
2. **Phase 2 only:** Known infection with human immunodeficiency virus (HIV), hepatitis C virus (HCV), or hepatitis B virus (HBV).
3. History of severe adverse reaction associated with a vaccine and/or severe allergic reaction (eg, anaphylaxis) to any component of the study intervention(s).
4. Receipt of medications intended to prevent COVID-19.

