5. Previous clinical or microbiological diagnosis of COVID-19.
6. Immunocompromised individuals with known or suspected immunodeficiency, as determined by history and/or laboratory/physical examination.

7. Bleeding diathesis or condition associated with prolonged bleeding that would, in the opinion of the investigator, contraindicate subcutaneous injection.
8. Women who are pregnant or breastfeeding.

Prior/Concomitant Therapy:

9. Previous vaccination with any coronavirus vaccine.
10. Individuals who receive treatment with immunosuppressive therapy, including cytotoxic agents or systemic corticosteroids, eg, for cancer or an autoimmune disease, or planned receipt throughout the study. If systemic corticosteroids have been administered short term (<14 days) for treatment of an acute illness, participants should not be enrolled into the study until corticosteroid therapy has been discontinued for at least 28 days before study intervention administration. Inhaled/nebulized, intra-articular, intrabursal, or topical (skin or eyes) corticosteroids are permitted.
11. Receipt of blood/plasma products or immunoglobulin, from 60 days before study intervention administration or planned receipt throughout the study.

Prior/Concurrent Clinical Study Experience:

12. Participation in other studies involving study intervention within 28 days prior to study entry and/or during study participation.

Other Exclusions

13. Investigator site staff or Sponsor employees directly involved in the conduct of the study, site staff otherwise supervised by the investigator.

Investigational Product, Dosage, and Mode of Administration:

hAd5-S-Fusion+N-ETSD, 1×10^{11} VP/dose, SC

Comparator: Placebo, SC

Duration of Treatment:

Subjects will be treated with hAd5-S-Fusion+N-ETSD or placebo on Days 1 and 22 (ie, 2 doses total of assigned intervention).

Duration of Follow-up:

Subjects are expected to participate for up to a maximum of approximately 2 years.

Evaluation of Endpoints:

Safety: Safety endpoints include assessments of reactogenicity events, AEs, and SAEs.

Efficacy: The first primary efficacy endpoint is COVID-19 incidence based on central laboratory or locally confirmed NAAT in subjects with no serological or virological evidence (up to 14 days after receipt of the last dose) of past SARS-CoV-2 infection.

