Final	100% (160 cases)	0.0227	Point estimate of VE \geq 50% and lower bound of the one-sided 97.73% CI for VE is $>$ 30%	90.0%

Should the primary endpoint(s) show success at either interim analysis, the Sponsor will decide after discussion with FDA to explore the options to expedite submission of the data for approval and possible early closure of the trial, with long-term follow up of patients already enrolled.

The study may be stopped early for futility (lack of benefit) at either interim analysis if the conditional power for the first primary endpoint is less than 5% ([Jennison 2000](#)).

A Poisson regression model with robust error variance will be used to estimate VE and its one-sided $(1-\alpha)100\%$ CI ([Zou 2004](#)).

Safety Analyses: Safety analyses will be based on the safety analysis population and subjects will be analyzed according to the actual study intervention received. Descriptive statistics will be provided for each reactogenicity endpoint for the active vaccine group and the placebo group. Local reactions and systemic events from Day 1 through Day 7 after each vaccination will be presented overall and by severity.

AEs and SAEs will be categorized according to the MedDRA terms. Descriptive statistics will be provided for each AE for the active vaccine group and the placebo group. For phase 2, AEs and SAEs will be presented for first vaccination through 7 days after last vaccination overall and by severity. For phase 3, AEs will be presented for first vaccination through 1 month after last vaccination and SAEs will be presented for first vaccination through 6 months after last vaccination overall and by severity.

Immunogenicity Analyses: Immunogenicity analyses will be based on the immunogenicity analysis population and subjects will be analyzed according to the actual study intervention received. Humoral immune response endpoints will be summarized descriptively for the vaccine and placebo groups by GMT, GMC, GMFR, percentage of subjects with titers greater than defined threshold(s), and neutralizing antibody titer demonstrated by ACE2 inhibition at baseline and specific times during the study, as noted in the Schedule of Events. Cellular immune response endpoints will be summarized

descriptively for the vaccine and placebo groups at baseline and specific times during the study, as noted in the Schedule of Events.

Figure 1: Study Schema

[figure not shown]

Table 8: Schedule of Events

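### Footnote a to the objectives table, read literally, removes participants who develop certain diseases after dosing from Primary Safety 2, contradicting the all-dosed safety population

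*Combined protocol and SAP*

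**What the plan says.** Marker a sits on the Objectives column header of the synopsis table of objectives, estimands and endpoints, not on any single row. The footnote reads: "HIV-positive and participants who develop immunosuppressive related diseases (eg, cancer, autoimmune disease) in Phase 3 will not be included in analyses of the objectives". It then makes one exception, for the specific exploratory objective. Exploratory objective 5, which concerns confirmed stable HIV disease and takes in all the safety, immunogenicity and efficacy endpoints, is the evident referent.

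Primary Safety 2 is a row of the same table. It addresses all subjects randomized in Phase 2/3, and its estimand begins: "In subjects receiving at least 1 dose of study intervention (safety analysis population), the percentage of subjects reporting". Its first AE item is "AEs from Dose 1 to 1 month after the last dose"; SAEs run to 6 months after the last dose.

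Under Statistical Methods, the Safety Analyses paragraph says: "Safety analyses will be based on the safety analysis population and subjects will be analyzed according to the actual study intervention received". On reporting periods it says: "For phase 3, AEs will be presented for first vaccination through 1 month after last vaccination and SAEs will be presented", the SAE period again ending 6 months after the last vaccination. Neither place mentions an exclusion for HIV or for disease arising during the study.

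HIV-positive people can be enrolled. Exclusion criterion 2 bars known HIV in Phase 2 only, and the note to inclusion criterion 3 points to Appendix 3 for the criteria that apply to stable HIV in Phase 3.

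**The concern.** A safety population is normally fixed by exposure: once dosed, a participant and all of that participant's events stay in. The footnote adds a condition that is settled only after dosing. A participant who develops a covered disease would leave the Primary Safety 2 analysis because of an event that the analysis exists to count. On the literal wording the new diagnosis goes, and so do that participant's other AEs, SAEs and any reactogenicity data, in either arm.

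The footnote also sets no time limit beyond the reference to Phase 3, while participation lasts up to about 2 years. A diagnosis made after the reporting windows close could therefore, if known at the time of analysis, remove events that had occurred inside them.

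At stake is whether the Phase 3 AE and SAE tables describe everyone dosed or a subset chosen partly by outcome.

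**Working it through.** No figure in the plan bears on this point, so the check is a comparison of texts.

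**Step 1. Scope of the footnote.** The marker is on the column header, so it reaches every row beneath, including Primary Safety. The only exception is one exploratory objective. Nothing in the footnote limits it to efficacy or immunogenicity.

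**Step 2. Scope of the safety passages.** The Primary Safety 2 estimand and the Safety Analyses paragraph agree with each other: at least one dose, analyzed by the intervention actually received, no further condition.

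**Step 3. Apply both rules to the same dosed participant.**

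| Dosed Phase 3 participant | Footnote a, literally | Primary Safety 2 and Safety Analyses | Other objective reporting their safety |
|---|---|---|---|
| Neither group | In | In | Not needed |
| HIV-positive at entry | Out | In | Exploratory 5 |
| Develops a covered disease after Dose 1 | Out | In | None |

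The second and third rows conflict, and none of the text supplied says which rule prevails.

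**Step 4. Compare the two conflicting rows.** HIV status at entry is a baseline characteristic. Exploratory 5 reports those participants on all safety endpoints, so the literal rule relocates them. New disease is a post-dose event. Exploratory 5 is confined to stable HIV, so the literal rule leaves those participants with no objective at all. The third row is therefore the substantive defect.

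**Step 5. Can the excluding event fall inside the reporting windows?** Yes. A new diagnosis up to 1 month after the last dose can be an AE. One up to 6 months after the last dose can enter the tables if it is serious. The event that triggers exclusion and the event to be counted can be the same.

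**Step 6. What is unclear at the edges.**
- The footnote does not define the diseases it covers. It names cancer and autoimmune disease as examples, but exclusion criterion 10 ties both to immunosuppressive treatment: "Individuals who receive treatment with immunosuppressive therapy, including cytotoxic agents or systemic corticosteroids, eg, for cancer or an autoimmune disease". The clause may cover every such diagnosis or only those that bring immunosuppression.
- Primary Safety 1 is not clearly affected. It concerns the first 200 subjects to 7 days after the last dose, known HIV is excluded in Phase 2, and the disease clause refers to Phase 3.

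**Step 7. Size.** The documents give no incidence of the covered diseases and no expected HIV prevalence. Any count would rest wholly on assumed rates, and a count of diagnoses would miss the other events removed with each participant. The contradiction stands without one, so none is given.

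**The case against.** The strongest reply is that the footnote was meant for efficacy and immunogenicity. Both passages that specify the safety analysis keep every dosed subject, and the Schedule of Events collects AEs and SAEs without regard to HIV or new disease. If analysts follow those passages, nothing is lost. Even on the literal reading the data exist and could be tabulated. This reading of the intent is plausible, but the footnote does not state it. Exploratory 5 also lists safety endpoints for HIV-positive participants, which makes it reasonable for an analyst to think their safety data belong only there.

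A second reply is that the text available is a synopsis with a schedule of events, and a fuller definition of populations may exist elsewhere. That is fair: the finding is that the conflict is unresolved in the text supplied.

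A third reply is that the HIV part is weak. This is accepted; those participants are reported separately.

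Some stronger readings should be resisted. A reader might infer that the sponsor plans to hide new cancers or autoimmune disease, or that these events will not be collected. The documents support neither. A reader might also infer a bias between arms or a calculable loss of ability to detect a signal. The footnote applies to both arms alike, nothing indicates the direction of any effect, and the planned analysis is descriptive: "Descriptive statistics will be provided for each AE for the active vaccine group and the placebo group".

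**Conclusion.** The contradiction is real and should be corrected. As written, footnote a and the Primary Safety 2 population cannot both apply. The disease-development clause is the main defect, because it conditions a primary safety analysis on a post-dose event that may be one of its own endpoints and leaves those participants reported nowhere else. The HIV clause is a lesser inconsistency: it moves participants to Exploratory 5.

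The number affected is unknown. It is zero if the safety passages govern, and not determinable from the documents if the footnote does. The conclusion rests on the literal scope of the footnote and on the text supplied. It does not assume that the sponsor intends the exclusion for safety, and it does not touch the sample size or power.

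**What to change.** Make two edits.

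1. Leave the rest of footnote a unchanged and append: *This exclusion does not apply to the Primary Safety objectives.*
2. Add to Safety Analyses: *All subjects who received at least 1 dose, including HIV-positive subjects and subjects who develop a disease after Dose 1, remain in the safety analysis population with all their events.*

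HIV-positive participants are still summarised under Exploratory 5 as well.

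The footnote should not be repaired by restating it as an exclusion from the efficacy objectives. The Sample Size paragraph defines the all-available efficacy population by randomization and at least one dose, and the evaluable population by completing the doses on schedule without major deviations judged to affect efficacy. Neither definition excludes HIV-positive participants or those with new disease. Rewording the footnote that way would write a post-randomization exclusion into the primary efficacy analysis. Footnote a should be reconciled with those definitions as a separate item.

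The cost of the safety fix is two sentences of text, with no new data or participants.

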The secondary primary endpoint is COVID-19 incidence based on central laboratory or locally confirmed NAAT in subjects with and without evidence of infection before vaccination.

Immunogenicity: Humoral immune response will be evaluated by S-binding IgG levels, N-binding IgG levels, and SARS-CoV-2 neutralizing antibody by cPass assay. Cellular immune response will be evaluated by SARS-CoV-2 specific memory CD4⁺ and CD8⁺ T-cell stimulation to N and S proteins.

Statistical Methods:

Primary Efficacy Endpoints: The first primary efficacy endpoint is COVID-19 incidence based on central laboratory or locally confirmed NAAT in subjects with no serological or virological evidence (up to 14 days after receipt of the last dose) of past SARS-CoV-2 infection and will be summarized in terms of $VE = 100\% \times (1 - IRR)$ [ratio of active vaccine to placebo].

After the above first primary endpoint is met, the second primary endpoint will be evaluated.

The second primary endpoint COVID-19 incidence based on central laboratory or locally confirmed NAAT in subjects with and without evidence of infection before vaccination.

Sample Size: The first 200 subjects randomized in the study will be included in phase 2. Phase 2 subjects will be included in the phase 3 portion of the study.

For phase 3, ~20,700 subjects will be randomized in a 1:1 ratio to either the hAd5-S-Fusion+N-ETSD or placebo. All randomized subjects who received at least one dose of study intervention will be included in the all-available efficacy population. The primary efficacy analysis will be based on the evaluable efficacy population which will include subjects in the all-available efficacy population who receive all planned doses of vaccine per schedule and have no major protocol deviations judged to effect efficacy.

The phase 3 sample size calculation is based on the primary efficacy endpoints and derived from the exact conditional test under the Poisson assumption which is appropriate for large trials where the illness rate is very low and hypothesis testing is based on a non-zero lower bound ([Chan 1998](#)). The null and alternative hypotheses for the primary efficacy analyses are:

Ho: $VE \leq 30\%$

Ha: $VE > 30\%$

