Under the assumption that the true VE is 60%, the primary efficacy analysis will require ~160 confirmed COVID-19 illness cases which will provide 90% power to conclude the true VE is $> 30\%$. Assuming the placebo illness rate is 1.3%, ~17,600 subjects will be required in the evaluable efficacy population for the primary efficacy analyses. These calculations are based a one-sided Type I error rate of 0.025. Assuming 15% of the all-available efficacy population will be unevaluable for the evaluable efficacy population, ~20,700 subjects will be sufficient to accrue ~17,600 subjects in the evaluable efficacy population.

Dependent upon the evolution of the pandemic, it is possible that the COVID-19 illness rate may change as the study progresses. An increase in illness rate could accelerate case accrual allowing the primary endpoints to be evaluated sooner, whereas a decrease in illness rate could slow down case accrual delaying the evaluation. At the time of the first interim efficacy analysis, the independent statistical team and DMC will evaluate the placebo illness rate. If the upper bound of the two-sided 95% CI for the observed placebo illness rate is less than the assumed placebo illness rate, then the sample size will be re-estimated by the independent statistician and DMC based on the observed placebo illness rate, and recommendations made to the Sponsor for final decision by the Sponsor.

Primary Efficacy Analysis: The primary efficacy endpoints will be analyzed at 2 interim analyses and the final analysis. The interim analyses will be conducted by the independent statistical team and reviewed by the independent DMC. The Lan-DeMets/O'Brien-Fleming alpha(α)-spending function ([Lan 1983, O'Brien 1979](#)) will be used to control the overall Type I error at one-sided 0.025 level. At each analysis, VE will be summarized by the one-sided $(1-\alpha)100\%$ CI. The table below summarizes the

information fraction (ie, % of total cases), nominal α , criterion for success, and cumulative probability of success if the true VE is 60% for each analysis:

Analysis	Information Fraction (% of Total Cases)	α	Success Criterion	Cumulative Probability of Success (if true VE=60%)
Interim #1	40% (64 cases)	0.0004	Point estimate of VE \geq 50% and lower bound of the one-sided 99.96% CI for VE is $>$ 30%	9.9%
Interim #2	70% (112 cases)	0.0073	Point estimate of VE \geq 50% and lower bound of the one-sided 99.27% CI for VE is $>$ 30%	61.5%

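### Severe COVID-19 has no place in the test sequence and no alpha, and the only VE model named gives a false bound if the vaccine arm has no severe cases

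*Combined protocol and SAP*

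**What the plan says.** All references are to the combined protocol and SAP.

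- **Rationale and Purpose, goal 5.** Lists fewer severe cases, shorter hospital stays, fewer ICU admissions and fewer deaths as a goal, and says the phase 2/3 trial was designed to test it.
- **Objectives table, Secondary Efficacy 1 and 2.** "To evaluate the efficacy of prophylactic hAd5-S-Fusion+N-ETSD against confirmed" severe COVID-19, first in subjects without evidence of earlier infection, then in subjects with and without it. The estimand is VE = 100% x (1 - IRR).
- **Statistical Methods, Primary Efficacy Endpoints.** "After the above first primary endpoint is met, the second primary endpoint will be evaluated". No later step follows.
- **Sample Size.** Null hypothesis VE of 30% or less, for the primary efficacy analyses. The sizing uses an exact conditional test. "These calculations are based a one-sided Type I error rate of 0.025".
- **Primary Efficacy Analysis.** O'Brien-Fleming-type spending with nominal alphas 0.0004, 0.0073 and 0.0227 at 64, 112 and 160 cases, with success criteria, all for the primary endpoints. "A Poisson regression model with robust error variance will be used to estimate VE" and its one-sided interval. Nothing is said about sparse or zero counts.

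The text supplied has no analysis section for the secondary efficacy endpoints and no projection of severe cases.

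**The concern.** There are two separate problems.

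**No error control.** Severe disease is a named goal and the first secondary objective, but nothing says whether it is tested, against what null, in what order or at what alpha. A favourable severe result could be reported only outside the 0.025 error control. The rule has to exist before the first look, because success at an interim may lead to expedited submission and early closure.

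**Misleading interval.** If the primary model is carried over to severe disease, which is the natural default because no other is named, it breaks down when the vaccine arm has no severe cases. The output would look like proven near-perfect protection even when the data cannot exclude zero efficacy.

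**Working it through.** **1. The plan's own figures.** Inputs (Sample Size): "the primary efficacy analysis will require ~160 confirmed COVID-19 illness cases"; true VE 60%; "Assuming the placebo illness rate is 1.3%, ~17,600 subjects will be required in the evaluable efficacy population"; 1:1 allocation; 15% unevaluable.

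- Given the total, a case falls in the vaccine arm with probability p = (1 - VE)/(2 - VE): 0.7/1.7 = 0.4118 under the null, 0.4/1.4 = 0.2857 under VE 60%.
- At 160 cases the exact critical value is 53 vaccine cases, with single-look power 91.2%.
- Over the three looks, exact cumulative power is 9.0 / 62.9 / 91.5%; the plan states 9.9 / 61.5 / 90.0%.
- The nominal alphas reproduce to four decimals.
- Evaluable N = 2 x 160/(0.013 x 1.4) = 17,582 (stated about 17,600). Randomized N = 17,600/0.85 = 20,706 (stated about 20,700).

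The primary design stands.

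**2. Zero cases under the named model.** Poisson regression with robust (HC0) variance was fitted in one package (statsmodels) with 8,800 subjects per arm and no vaccine-arm cases. For 0 v 10 the log-IRR keeps falling: -11.4 after 10 iterations, -21.4 after 20, -31.8 when the software stops. The robust SE stays at 0.316, which is the square root of 1/10, because the empty arm adds nothing to it. The printed interval therefore collapses onto 100%.

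Exact one-sided 97.5% lower bound with 0 v n cases: upper limit for p is 1 - 0.025^(1/n), and VE = 1 - p/(1 - p).

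| Vaccine v placebo | Printed lower bound | Exact lower bound |
|---|---|---|
| 0 v 1 | about 100% | -3,800% |
| 0 v 5 | about 100% | -9% |
| 0 v 10 | about 100% | 55.4% |

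**3. How often the vaccine arm would have no severe cases.** Expected placebo cases at the final analysis: 8,800 x 0.013 = 114.4. The severe share s is an assumption, because the documents give none. P(zero) = exp(-114.4 x s x (1 - severe VE)).

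| s | Placebo severe cases | VE 60% | VE 80% | VE 90% |
|---|---|---|---|---|
| 3% | 3.4 | 25% | 50% | 71% |
| 5% | 5.7 | 10% | 32% | 56% |
| 10% | 11.4 | 1% | 10% | 32% |

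**4. What a controlled test could deliver.** With no vaccine cases, VE of 0% or less is rejected if 0.5^n is at most alpha. This needs 6 placebo severe cases at 0.0227, 8 at 0.0073 and 12 at 0.0004. Power against VE of 0% or less uses the exact binomial test averaged over a Poisson total. Expected placebo cases at each look are total/1.4, and s runs from 3% to 10%.

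| Look (placebo cases) | Alpha | VE 60% | VE 80% | VE 90% |
|---|---|---|---|---|
| Interim 1 (45.7) | 0.0004 | about 0% | at most 0.1% | at most 0.2% |
| Interim 2 (80) | 0.0073 | 0.1-9% | 0.2-24% | 0.3-37% |
| Final (114) | 0.0227 | 4-30% | 8-63% | 10-82% |

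**The case against.** The best defence is that secondary endpoints reported as estimates only are a legitimate design. The severe objectives carry an estimand and no success criterion, and no secondary claim is promised. Goal 5 is a statement of rationale, not an analysis rule. This stands to the extent that labelling the endpoints descriptive would remove the ambiguity. It does not explain why the text says neither.

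The Poisson sentence belongs to the primary analysis, where about 46 vaccine-arm cases are expected (114.4 x 0.4) and no zero-cell problem arises. Strictly, severe disease has no assigned method at all. That also stands: the zero-case problem is conditional on the model being carried over.

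Three stronger readings are tempting but not supported:

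- A reader might infer a confirmatory intent because Secondary 1 and 2 are to be evaluated while Secondary 3 and 4 are to be described. But exploratory objectives 1 to 4 also start with that first verb, and their humoral and cellular endpoints are summarized descriptively.
- A reader might put the family-wise error at 4 x 0.025 = 10% across the four secondaries. The plan proposes no such tests.
- A reader might call zero vaccine-arm severe cases the expected result. At the plan's own VE of 60% the chance is 1-25%; it passes one half only with a small severe share and a high severe VE.

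Finally, the text supplied cites appendices that are not included, and some pages were removed. The absence is established only for the supplied text.

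**Conclusion.** The point holds, in two parts that should be kept apart.

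The first rests on no assumed figure: in the text supplied, severe disease has no step, hypothesis or alpha, so no error-controlled claim can be made about it.

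The second is conditional. If the named Poisson model is used and the vaccine arm has no severe cases, the interval is wrong, and wrong in the vaccine's favour. How often that happens depends on the assumed 3-10% severe share and the true severe VE: from 1% to 71% over the range shown. The zero-case problem adds nothing to the lack of alpha, and neither part touches the primary analyses, whose figures reproduce.

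**What to change.** 1. **Interval.** For both severe endpoints, report VE with the exact conditional (Clopper-Pearson) interval in place of the robust Poisson Wald bound. It belongs to the same family as the plan's sample-size method.
2. **Sequence.** After both primaries succeed, test severe COVID-19 in infection-naive subjects, then in all subjects, with H0: VE of 0% or less. State that if the primaries succeed early, severe disease is tested at the final or latest planned look, under its own O'Brien-Fleming-type spending at overall one-sided 0.025, with information measured in severe cases.
3. **Alternative.** If no severe claim is wanted, label both severe endpoints descriptive and keep the exact interval. This gives up a controlled conclusion on goal 5.

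The cost is a few sentences in the SAP and a standard exact interval. Because the new steps open only after both primaries succeed, they take no alpha from them. The SAP should state the downside: under the assumed severe shares, power at the final look is limited (4-30% at severe VE 60%, up to 82% at 90%). It is at most about 37% at interim 2 and close to nil at interim 1, so early closure would leave little chance of a severe-disease conclusion.
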